**Restoration:**

- Overall VAS Score: Up to 3 intra-operative VAS measurements are recorded. If a patient feels even the slightest amount of pain during the procedure, they are instructed to raise their hand and the treatment would be paused. The patient will then be asked to fill in the VAS form. The procedure could then be continued. After the conclusion of the cavity preparation, the patients are asked to mark one last VAS rating indicating the overall pain of the procedure.

**7.2 Study Data**

Patients included in the study are adults 19-65 years old who had at least two cavity preparations of the same type, with the same approximate size lesion. Excluded patients include children, people with language barriers, pregnant women, immune compromised patients compromised (No bronchitis, no sinus infection, no ear infection, ect...), patients with heart disease, uncontrolled hypertension (high blood pressure), cardiac arrhythmia, and patients whose teeth amalgam restorations were in close proximity to the lesion.

When approved to be in the required parameters subject to the appropriate requirements, the paperwork will be read, signed and collected from each eligible subject. Once all the paperwork is filled out the study will then be started.

**7.2.1 Collection of data**

**7.3 Randomization and Blinding**

The patient information (including name, age ect.) will not be associated with the results of the study that will be included in future articles. [name] will only have record and know what results go with what patients so confidentiality is kept.

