### **Explanation of VAS analysis**

The VAS scale will be presented to the patients using a standard explanation (zero, indicating no pain at all, to 100, representing the ‘worst pain patient had ever felt’). Patients will be asked to place a vertical line on the VAS scale to indicate his/her discomfort status. They are encouraged to stop the treatment if they encounter any pain. The number of hand raises, as defined by the protocol, will be recorded and analyzed (small and medium/large preparations are analyzed separately), represent the number of times during the procedure the patient felt sufficient discomfort to stop the procedure.

VAS data will be assessed by the following assumptions: The 'lower' the average score, the 'better' the mode of treatment. Once the patient marks their vertical line on the scale, a precise measurement, in millimeters, was taken from the “zero” line of the VAS scale to where the patient marked their line.

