## 7 STUDY PROCEDURES

### 7.1 Workflow

This study will consist of two procedures. Both procedures will be performed on the same patient. Both procedures are cavity preparations. The tooth is chosen and the first procedure is started. The first one will be done with LLLT protocol prior to using the higher power to perform the cavity preparations. The second preparation will be done without LLLT first and thus using the higher power laser for cavity preparation from the beginning.

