#### **Laser Preconditioning:**

- A. Laser Desensitization/ preconditioning procedure
  - a. Randomly select one tooth to have laser preconditioning performed on it
    - Preconditioning is using some LLLT on the tooth without expecting much, if any, ablation of the tooth.
    - For preconditioning, the setting is 0.25 Watt, 50Hz, 0% water, 0% air, H mode.
  - b. Aim fibre-optic tip perpendicular to the surface of cervical portion of tooth
  - c. Ensure that a 2mm distance between the end of the fiber optic tip and the surface is maintained
  - d. Go back and forth with the fibre-tip over a 2mm line for the number of seconds indicated
  - e. Prep the cavity on the first tooth (settings to follow)
  - f. Prep the cavity on the second tooth, without laser preconditioning

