#### **Preparation of Lesion:**

- A. Laser ablation- Small Preparation
  - a. Waterlase MD settings: 4.5W, 15Hz, 65% air, 60% water
  - b. Prepare cavity preparation using preferred technique
  - c. If the patient indicates sensitivity,
    - Halt the procedure
    - Have the patient mark the VAS form,
    - Offer anaesthetic; if refused, continue using the same settings
- B. Laser ablation- Small and Medium Preparation
  - a. Waterlase MD settings: 2W, 15Hz, 65% air, 60% water
  - b. Prepare cavity preparation using preferred technique
  - c. If the patient indicates sensitivity, either
    - Halt the procedure

- Have the patient mark the VAS form,
- Offer anaesthetic; if refused, continue using the same settings

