## **9.2 Bias Minimization**

All subjects meeting the specified eligibility criteria will be enrolled in the study until all spots are filled up.

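### With no masking, no matched control pass and LLLT always given first, a lower pain score on the LLLT tooth cannot be attributed to LLLT

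*Protocol*

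**What the plan says.** **Masking.** The full content of Protocol Section 7.3 concerns privacy: "The patient information (including name, age ect.) will not be associated with the results of the study", and one role alone will "know what results go with what patients so confidentiality is kept". Section 9.2 Bias Minimization consists of one measure: "All subjects meeting the specified eligibility criteria will be enrolled in the study until all spots are filled up". Neither section says whether the patient, the operator or the person measuring the VAS line is kept unaware of the condition.

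**The two conditions.** Under Laser Preconditioning in Section 7.1, one tooth is picked at random for a distinct step with its own settings ("For preconditioning, the setting is 0.25 Watt, 50Hz, 0% water, 0% air, H mode"). The tip is held 2 mm away and moved over a 2 mm line. For the other tooth the instruction is "Prep the cavity on the second tooth, without laser preconditioning". The Workflow text of Section 7.1 puts the LLLT tooth first and adds: "The second preparation will be done without LLLT first and thus using the higher power laser for cavity preparation from the beginning". No substitute step is described for the control tooth. The cutting itself is left open: "Prepare cavity preparation using preferred technique".

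**The outcomes.** Section 4.1 says: "Patients will be asked to place a vertical line on the VAS scale to indicate his/her discomfort status". Hand raises are also counted and analysed. Under Restoration in Section 4.1, a patient who never raises a hand is assigned an overall VAS of zero.

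**The question.** Section 3 names proof of laser analgesia as the principal objective. It then asks whether LLLT improves analgesia, which is what the two-tooth comparison is for.

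**The concern.** Each patient experiences both conditions while awake. One has an extra laser step before cutting and the other does not. Section 13.2.1 has the investigator explain every aspect of the study, so a patient who notices the step, or knows the order, can work out which tooth was meant to hurt less.

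That patient then supplies all the efficacy data. The hand-raise threshold is very low (any pain at all), and under the Section 4.1 rule an expectation that merely holds back a hand raise becomes an overall score of zero.

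Three explanations other than LLLT travel with the LLLT tooth: expectation, the extra step before cutting, and being treated first. The operator also knows the condition and has latitude in technique. At stake is whether a favourable difference between teeth can be reported as an LLLT effect.

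**Working it through.** **1. Can the design separate LLLT from the alternatives?** The two teeth compare as follows under Sections 4.1 and 7.1.

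| Feature | LLLT tooth | Control tooth |
|---|---|---|
| Pass before cutting | yes, own settings | none |
| Position in the visit | first | second |
| Operator aware of condition | yes, sets the laser | yes |
| Masking of patient | none stated | none stated |
| Source of outcome | patient | patient |

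LLLT emission, the presence of a pass and the order of treatment all change together. No analysis of the VAS forms can pull them apart, because no tooth has one without the others.

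**2. Number of pairs.** The formula in Section 9.1, with 1.96 used throughout, N = 50, p = 0.5 and A = 0.025, gives

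n = (1.96² × 50 × 0.25) / (0.025² × 50 + 1.96² × 0.25) = 48.42,

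which reproduces the plan's figure of about 48. (The printed substitution has 1.69 in the numerator, which would give 36.00; that is a separate matter.) The formula is for a proportion, so it supplies no SD for VAS differences. With one pair per patient, 48 is an upper bound: Section 6.1.2 leaves out procedures finished under injection, and Section 4.1 analyses small and medium/large preparations separately, for hand raises at least.

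**3. Illustration of size.** Inputs:
- n = 48 pairs (Section 9.1), and 24 pairs as an illustrative reduced number.
- s, the SD of within-patient VAS differences: 20, 25 or 30 mm (assumed).
- b, a shift due only to expectation: 2, 5 or 10 mm (assumed).
- True LLLT effect: zero. Test: paired t, two-sided 5% (assumed).

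The chance of a significant result favouring LLLT is P(T > t₀.₉₇₅,ₙ₋₁), where T is noncentral t with n − 1 degrees of freedom and noncentrality b / (s/√n). For n = 48 the critical value is 2.012, and s/√n is 2.887, 3.608 and 4.330 mm. For b = 5 the noncentralities are 5/2.887 = 1.732, 5/3.608 = 1.386 and 5/4.330 = 1.155.

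| Pairs | Shift | SD 20 | SD 25 | SD 30 |
|---|---|---|---|---|
| 48 | 0 mm | 0.025 | 0.025 | 0.025 |
| 48 | 2 mm | 0.100 | 0.078 | 0.066 |
| 48 | 5 mm | 0.396 | 0.273 | 0.204 |
| 48 | 10 mm | 0.924 | 0.775 | 0.619 |
| 24 | 5 mm | 0.216 | 0.154 | 0.120 |

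For scale, 48 pairs have 80% power at 0.413 SD, which is 0.413 × 20 = 8.3 mm to 0.413 × 30 = 12.4 mm. A 10 mm expectation shift would therefore be about the size of effect the trial could detect.

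**The case against.** **The size is assumed.** This stands. The documents give neither an SD nor an expectation effect, and a 1 mm shift would raise the rate only to about 4-5% with 48 pairs. Fewer pairs lower the rates, and many tied zeros under the Section 4.1 rule would fit a t-test poorly. The table shows how the error grows with the shift. It does not estimate the bias in this trial. The argument in step 1 needs none of these values.

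**A matched pass alone would not mask the patient.** This stands too. If LLLT always comes first and the patient is told so, the first pass is known to be active however the second one looks. Nothing in the documents shows that a non-emitting pass would look, sound or feel the same, and its length cannot be fixed from the text because no number of seconds is given. Order has to be randomised as well, and the duration written down.

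**Stronger readings that the documents do not support:**
- A reader might infer that the operator decides when to pause. Sections 4.1 and 7.1 tie the pause to the patient's hand raise or sign of sensitivity. The operator's documented discretion is in technique.
- A reader might infer that the whole trial fails. Masking between teeth does not touch the principal objective in Section 3, and the synopsis objective does not mention LLLT.
- A reader might infer a declared open-label design. The protocol never says so. The lack of masking follows from the procedures it describes, and that patients recognise the LLLT step is likely but not stated.

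**An analysis plan might cover it.** Masking and the control procedure are matters of conduct, and the protocol has its own section for them. A later analysis plan could not supply them.

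**Conclusion.** The point holds for the question of whether LLLT improves analgesia. As written, Sections 7.1, 7.3 and 9.2 leave a between-tooth difference open to expectation, the extra step and treatment order, and all the efficacy data come from an unmasked patient.

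Under the stated assumptions, and with no true effect, the rate of a false finding for LLLT rises from 2.5% to about 7-10% for a 2 mm shift, 20-40% for 5 mm and 62-92% for 10 mm with 48 pairs. With 24 pairs, 5 mm gives 12-22%. These figures cover expectation alone. The size and direction of any order effect cannot be judged from the documents. The change should be made before enrolment, because the analysis cannot repair it afterwards.

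**What to change.** In Sections 7.1 and 7.3:

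1. Give the control tooth a matched pass before preparation, with the same tip, distance and time but no LLLT emission. State the pass duration.
2. Randomise which tooth is treated first as well as which tooth gets LLLT, remove the fixed order from Section 7.1, and do not tell the patient which pass is active.
3. Use one fixed script for both teeth.
4. Label VAS forms by tooth code, so that existing staff can make the millimetre reading without the allocation.
5. State that the operator remains unmasked.

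If the sponsor declines the matched pass, Section 7.3 should say that the LLLT comparison is unmasked, and the LLLT conclusion should be limited to match. Items 2 (random order), 3 and 4 are still worth making.

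The cost is a short added chair time per patient (not quantifiable until the pass duration is given), consent wording that one pass is inactive, and minor form handling, including a reader other than the operator. No laser setting or rescue rule changes.

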**7.4 Procedures for Study Closure**

**7.4.1 Routine study close-out**

The study will end when [name] has obtained all data necessary. Study close-out will follow [name] standard procedures and may include, but is not limited to, review of regulatory documents, collection of completed case report forms, reconciliation of study records, removal or destruction of ancillary study supplies, and

informing the Investigator of remaining obligations (e.g., record retention, final report submission to the IRB, financial disclosure updates, etc.).

#### **7.4.2 Suspension or premature termination of the study**

This study may prematurely terminate at any time because of a regulatory authority decision, a change in opinion of the IRB, or at the discretion of the Investigator or Sponsor. If this trial is temporarily suspended or prematurely discontinued, [name] will notify the Investigator(s) and provide instructions. If the study is temporarily suspended, [name] will provide guidance on timing and procedures for resuming the study. If the study is prematurely discontinued, all study materials must be collected and all study forms completed to the extent possible.

## **8 DATA QUALITY ASSURANCE**

The study site will be responsible for the accuracy of the data collected.

## **9 STATISTICAL METHODS**

### **9.1 Determination of Sample Size**

The total number of individual subjects is expected to reach approximately forty-eight patients. This estimate is based on the number of teeth that need to be done.

$$n = \frac{c^2 * N * p * (1-p)}{(A^2 * N) + (c^2 * p * [1-p])}$$

**n** = the sample size required

**N** = the target population (50)

**p** = is the average proportion of records expected to meet the various criteria (1-p) is the average proportion of records not expected to meet the criteria if unknown choose 50% you do not want more than 50% you actually prefer to be way under but it is always better to estimate higher so you make sure you get enough results for your study.

**A** = is the margin of error deemed to be acceptable (2.5%)

**c** = is a mathematical constant defined by the Confidence Interval chosen ie (how sure we need to be of the result)

To be 95% sure of the result the constant **c** = 1.96 which is always given.

A narrower margin of error requires a larger sample size. Our margin of error is 2.5%.

$$n = \frac{1.69^2 * 50 * .50 * (1-.50)}{(.025^2 * 50) + (1.96^2 * .50 * [1-.50])}$$

$$n = 48.42$$

Which will get our result of about 48 patients

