## 3 STUDY OBJECTIVES

The principal objective of this study is to prove the phenomenon of laser analgesia. Traditionally before a cavity preparation is performed, the doctor will use local anesthetic (Needle Injection) before using rotary instrument to do a cavity preparation. The study involves using the Er,Cr=YSGG Laser to perform cavity preparation without giving any injection anesthesia. VAS (Visual Analog Scale) will be used to have patients rate the laser

cavity preparation procedure to show there is laser analgesia. On each patient subject that has two similar size cavities of the same classification, either Class I or Class V, on similar teeth. Two different laser protocols will be used. One includes Low Level Laser Therapy (LLLT) to condition the pulp producing analgesia before using higher power to perform the cavity prep. The other protocol will skip the LLLT setting and prepare the cavity with the higher power to perform the cavity prep. The design of the study is to find out if there is laser analgesia and if LLLT makes a difference in providing better analgesia. The VAS forms from each procedure will be used to show there is laser analgesia and potentially cavity preparations can be performed by using the laser without the need to give injection anesthesia first.

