## **5 STUDY POPULATION**

### **5.1 Sample Size and Target Study Population**

#### **5.1.1 Sample size**

The total number of individual subjects is expected to reach approximately forty-eight patients. This estimate is based on the number of teeth that possibly will need to have this surgery out of the people that come to the office.

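### Section 9.1 adds to a feasibility-based 48 patients a 95% / 2.5% margin of error that describes no outcome the trial defines and does not hold beyond a closed group of 50

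*Protocol*

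**What the plan says.** The protocol gives two bases for about 48 patients.

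- **Feasibility.** Section 5.1.1 rests the number on the "number of teeth that possibly will need to have this surgery out of the people that come to the office". Section 9.1 opens the same way: "This estimate is based on the number of teeth that need to be done".
- **A survey formula.** Section 9.1 then applies a sample size formula for one proportion with a finite population. N is "the target population (50"), and p "is the average proportion of records expected to meet the various criteria", set to 50%. The confidence level is 95% with c = 1.96. The section concludes: "A narrower margin of error requires a larger sample size. Our margin of error is 2.5" (per cent), with a result of 48.42.

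The design is described elsewhere. Section 3 states the principal objective as establishing laser analgesia and adds the LLLT question: "The design of the study is to find out if there is laser analgesia and if LLLT makes a difference". Section 7.1 has both preparations done in the same patient, one with LLLT first and one without. The VAS explanation in section 4.1 says that "a precise measurement, in millimeters, was taken from the" zero line to the patient's mark. It judges treatment by the average score and also counts hand raises. Section 9.3 plans to analyse the VAS forms from each procedure.

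**The concern.** The formula answers how many records to draw from a list of 50 to estimate what share meet some criteria. Neither the records nor the criteria are tied to anything the trial measures. The outcomes are a continuous score and a count, and the LLLT question is a comparison within patients. A margin for one proportion carries over to none of these.

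The 2.5% is an affirmative claim of precision, not a detail left to an analysis plan. An ethics committee or journal reader would take from section 9.1 that the trial's result will be known to within 2.5% with 95% confidence. For the general conclusion the trial seeks, that is not so.

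**Working it through.** **Inputs, all from section 9.1:** N = 50, p = 0.50, A = 0.025, c = 1.96.

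**1. The plan's own figure.** n = c²·N·p(1−p) / [A²·N + c²·p(1−p)]
- Numerator: 3.8416 × 50 × 0.25 = 48.02
- Denominator: 0.000625 × 50 + 3.8416 × 0.25 = 0.03125 + 0.9604 = 0.99165
- n = 48.02 / 0.99165 = 48.42, as stated.

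The worked line shows "1.69^2 * 50 * .50 * (1-.50") in the numerator. Taken literally, 1.69 gives 35.70 / 0.99165 = 36.00. The stated result therefore used 1.96, and the slip did not enter it.

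**2. What drives n.** One input is changed at a time:

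| Change | n |
|---|---|
| N = 100 | 96.04 / 1.0229 = 93.9 |
| N = 1000 | 960.4 / 1.5854 = 605.8 |
| No finite population | 0.9604 / 0.000625 = 1,537 |
| p = 0.1 (N = 50) | 17.287 / 0.37699 = 45.9 |
| A = 5% (N = 50) | 48.02 / 1.0854 = 44.2 |

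Doubling the margin removes about four patients, while doubling N nearly doubles n. The answer lies near 50 because 50 was put in.

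**3. A yes/no result generalised beyond the 50.** Half-width = 1.96 × √(0.25/48) = 0.141, or ±14.1 percentage points at p = 0.5. That is more than five times 2.5.

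**4. The closed group of 50.** The finite-population factor for 48 of 50 is √(2/49) = 0.202, so 14.1 × 0.202 is about 2.9 points (2.8 with √(2/50)). The stated margin is approached only when 48 people are used to describe themselves and two others.

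**5. The within-patient VAS comparison.** The protocol gives no SD of the paired difference, so the result is in SD units. For 48 evaluable pairs and a paired t interval, half-width = t(0.975; 47)/√48 = 2.012/6.928 = 0.29 SD. As an illustration of a split by preparation size, 24 pairs give 2.069/4.899 = 0.42 SD. On an assumed SD of 15–30 mm (not in the protocol), 0.29 SD is 4.4–8.7 mm. These figures generalise beyond the patients enrolled. They are approximate because section 4.1 scores patients who never raise a hand as zero, so many differences may be exactly zero.

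**The case against.** The strongest reply stays inside the protocol's own frame. If the target really is a closed group of 50, high precision follows for almost anything. A 0–100 score has an SD of at most about 50, the same bound as a proportion at p = 0.5, so the mean VAS of one procedure would be known to within about 2.9 points. On the same assumed SD of 15–30 mm, the paired difference would be known to within 0.290 × 0.202 × SD, about 0.9–1.8 mm. This stands. A reader might infer that the design lacks such precision for every outcome under every reading, and the document does not support that. The reply does not rescue section 9.1, however. Section 3 seeks a general phenomenon, not a description of 50 people, and the 2.5% is nowhere expressed on the VAS scale.

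A second reply is that section 9.3 hints at a proportion free of pain or injection. None is defined. If one were, the margin beyond the 50 would be up to about 14 points.

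Third, the paired t calculation is a reviewer's choice: section 9.3 names no test, and an analysis plan may exist. This also stands. The calculation covers only the LLLT question, not the principal objective, so it belongs in the protocol at most as one conditional sentence.

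Finally, no stopping rule, test or decision uses the 2.5%. That limits the consequence to what readers are told.

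**Conclusion.** The 95% / 2.5% statement should not stand. It comes from a one-proportion formula with no matching outcome. Its n of about 48 mostly reflects the choice N = 50, and it could hold, even approximately, only for a closed group of that size. Beyond those 50 people the corresponding figure for a yes/no result is about ±14.1 points at p = 0.5. This rests on the protocol's own inputs and on reading section 3 as seeking a conclusion wider than the patients treated.

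Two stronger readings are tempting and are not supported:
- **That 48 patients are too few.** The protocol gives no SD and no target difference, so adequacy cannot be judged either way, and feasibility is a stated basis in its own right.
- **That 48.42 is miscalculated.** It reproduces with c = 1.96. The 1.69 may be a misprint or a misread digit and carries no weight.

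The point is worth correcting because the claim is wrong as written, but it changes no patient number.

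**What to change.** In section 9.1, keep about 48 patients on the feasibility basis already given there and in section 5.1.1. Delete the formula, its worked line and the 2.5% / 95% statement.

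If a precision statement is wanted, one conditional sentence suffices:

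> If VAS with versus without LLLT is compared as a mean within-patient difference and generalised beyond the patients enrolled, 48 evaluable pairs give an approximate 95% CI half-width of 0.29 SD of the paired difference (paired t, roughly normal differences); precision is lower with fewer evaluable pairs or if preparation sizes are analysed separately.

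State beside it that this covers the LLLT comparison only and makes no precision claim for laser analgesia as such.

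The change is wording only and adds no patients. Its downside is that the stated precision becomes less favourable.

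### Section 9.1 prints 1.69 for 1.96 in its worked sample-size line, and rounding 48.42 down to 48 narrowly misses the stated 2.5% margin

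*Protocol*

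**What the plan says.** Protocol Section 9.1 (Determination of Sample Size) gives a formula for estimating a proportion in a finite population and fixes its inputs in the text:

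- N is "the target population (50"), with no unit attached.
- p is a proportion of records meeting criteria, with the advice "if unknown choose 50" per cent; 0.50 is used.
- The constant for 95% confidence is "1.96 which is always given".
- On the margin: "A narrower margin of error requires a larger sample size. Our margin of error is 2.5" per cent.

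The substitution then has "1.69^2 * 50 * .50 * (1-.50") as its numerator, while the denominator uses 1.96. The stated result is 48.42, followed by "Which will get our result of about 48 patients".

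The Synopsis repeats forty-eight without qualification. Section 5.1.1 says: "The total number of individual subjects is expected to reach approximately forty-eight patients". Both 5.1.1 and 9.1 also say that the estimate rests on a number of teeth.

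**The concern.** This is the protocol's only numerical justification of its size, and two things in it do not agree.

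First, the displayed equation is false as printed. The constant in the numerator is not the one the section defines, and anyone who evaluates the line gets a much smaller number than the one stated beneath it.

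Second, the formula returns the smallest n that achieves the chosen margin. A fractional minimum has to be rounded up. The protocol rounds down and leaves the margin unchanged, so the adopted size and the stated precision do not match.

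At stake is whether the section can be checked and whether its precision statement is true. A reader in ethics review or at a journal who recomputes the line may doubt the whole justification because of one wrong pair of digits.

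**Working it through.** **Inputs**, all from Section 9.1: N = 50, p = 0.50, A = 0.025, c = 1.96 as defined, 1.69 as printed in the numerator.

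**Formula:** n = c²·N·p(1−p) / [A²·N + c²·p(1−p)]

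**1. The plan's own figure, with the defined constant in both places**

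- Numerator: 1.96² × 50 × 0.25 = 3.8416 × 12.5 = 48.02
- Denominator: 0.025² × 50 + 1.96² × 0.25 = 0.03125 + 0.9604 = 0.99165
- n = 48.02 / 0.99165 = 48.42, which is the stated result.

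**2. The line as printed (1.69 above, 1.96 below)**

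- Numerator: 1.69² × 50 × 0.25 = 2.8561 × 12.5 = 35.70
- Denominator unchanged: 0.99165
- n = 35.70 / 0.99165 = 36.00, not 48.42.

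**3. Could 1.69 have been intended throughout?**

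- Denominator: 0.03125 + 2.8561 × 0.25 = 0.03125 + 0.71403 = 0.74528
- n = 35.70 / 0.74528 = 47.90, which is also not 48.42.

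Of the three, only 1.96 in both places reproduces the stated figure, so the calculation was done with the right constant and the digits were swapped when it was written out.

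**4. The margin that a given n delivers**

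Solving the same formula for A gives A = c·√[p(1−p)(1/n − 1/N)] = 0.98·√(1/n − 1/50).

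| n | 1/n − 1/50 | Margin |
|---|---|---|
| 48 | 0.00083333 | 0.98 × 0.028868 = 2.83% |
| 49 | 0.00040816 | 0.98 × 0.020203 = 1.98% |

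So 48 misses 2.5% and 49 meets it.

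**5. Sensitivity to the form of the finite-population correction**

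With N − 1 in the correction, the required n is 48.46, and the margins are 2.86% at 48 and 2.00% at 49. The conclusion is the same.

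**The case against.** The strongest reply is that nothing of substance depends on either error. The section defines 1.96, prints it in the denominator and reports the number that 1.96 gives, so correcting the digits changes no planned figure. The rounding gap is a single patient, and both 9.1 and 5.1.1 soften 48 with a word of approximation. The margin also describes a proportion of records, whereas Section 9.3 plans to analyse VAS forms, which Section 4.1 measures in millimetres. All of this stands, and it is why the point is minor. It does not remove the point: the displayed equation is still wrong, the Synopsis gives forty-eight without the qualifier, and the 2.5% is nowhere softened.

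A reader might be tempted to go further in four ways that the protocol does not support.

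- **That 36 is the real requirement, or that the sample size was miscalculated.** Step 1 shows otherwise: 48.42 is correct for the stated inputs.
- **That 48 patients leave the trial's main comparison too imprecise.** The margin belongs to a proportion that no stated analysis estimates. Moving from 2.5% to 2.83% says nothing about the precision of a VAS difference.
- **That n is really a count of teeth, so that patient numbers are wrong by a factor of two.** Section 9.1 opens and closes by counting patients. The reference to teeth can be read as the source of the estimate, and 5.1.1 explains it that way. What remains open is narrower: N = 50 is never given a unit.
- **That losses make the shortfall large.** With N at only 50 the margin does widen quickly as patients are lost, but the protocol gives no expected loss. Such figures would illustrate dropout; they would not show an error in 9.1.

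**Conclusion.** The point holds as a minor correction in two parts. The worked line in Section 9.1 contains a transcription slip: it equals 36.0 as printed, while the stated 48.42 is right with c = 1.96 throughout. Independently of that slip, 48 is one patient below the minimum for the stated margin; it delivers 2.83%, and 49 delivers 1.98%.

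This takes the protocol's formula and its inputs as given. Whether a proportion formula is a suitable basis for a within-patient VAS comparison is a separate question and is not judged here. The first part also assumes that the 1.69 stands in the sponsor's own file and did not arise when the text was extracted from PDF; the second part does not depend on this. What N = 50 counts is an open question for the sponsor, not a demonstrated error.

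**What to change.** In Section 9.1:

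- Print 1.96 in place of 1.69 in the numerator, after checking the digits in the source file.
- Keep 48 patients and restate the margin as about 2.8%. If 2.5% is to be kept, state 49 patients in 9.1, 5.1.1 and the Synopsis.
- State what N = 50 counts, and reconcile the remark that the estimate is based on teeth with the reading of n as patients.
- If the formula is withdrawn because the planned analysis is of VAS scores and not of a proportion, withdraw the 2.5% figure with it; a restated margin would then serve no purpose.

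The cost is one corrected line, one clarifying sentence and a slightly less favourable stated margin. No extra patient is needed if the margin is restated; one is needed if 2.5% is kept.
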